7.6 PROHIBITED MEDICATIONS, TREATMENTS, AND PROCEDURES

Treatment with (list specific drugs) will not be permitted unless discussed with and approved by the PI.

- Immunosuppressant including oral and parenteral corticosteroids (topical and stable dose inhaled corticosteroids are acceptable)or modulating drugs.
- Non-steroidal anti-inflammatory drugs
- Any blood thinning medications, aspirin or other medications affecting blood clotting.

7.7 PROPHYLACTIC MEDICATIONS, TREATMENTS, AND PROCEDURES

Not applicable

7.8 RESCUE MEDICATIONS, TREATMENTS, AND PROCEDURES

Not Applicable

7.9 PARTICIPANT ACCESS TO STUDY AGENT AT STUDY CLOSURE

Not applicable.

8 ASSESSMENT OF SAFETY

8.1 SPECIFICATION OF SAFETY PARAMETERS

8.1.1 DEFINITION OF ADVERSE EVENTS (AE)

Adverse event means any untoward medical occurrence associated with the use of an intervention in humans, whether or not considered intervention-related (21 CFR 312.32 (a)).

8.1.2 DEFINITION OF SERIOUS ADVERSE EVENTS (SAE)

Serious adverse event or serious suspected adverse reaction. An AE or suspected adverse reaction is considered "serious" if, in the view of either the investigator or sponsor, it results in any of the following outcomes: death, a life-threatening adverse event, inpatient hospitalization or prolongation of existing hospitalization, a persistent or significant incapacity or substantial disruption of the ability to conduct normal life functions, or a congenital anomaly/birth defect. Important medical events that may not result in death, be life-threatening, or require hospitalization may be considered serious when, based upon appropriate medical judgment, they may jeopardize the patient or subject and may require medical or surgical intervention to prevent one of the outcomes listed in this definition. Examples of such medical events include allergic bronchospasm requiring intensive treatment in an emergency room or at home, blood dyscrasias or convulsions that do not result in inpatient hospitalization, or the development of drug dependency or drug abuse.

8.1.3 DEFINITION OF UNANTICIPATED PROBLEMS (UP)

OHRP considers unanticipated problems involving risks to participants or others to include, in general, any incident, experience, or outcome that meets **all** of the following criteria:

- Unexpected in terms of nature, severity, or frequency given (a) the research procedures that are described in the protocol-related documents, such as the IRB-approved research protocol and informed consent document; and (b) the characteristics of the participant population being studied;
- Related or possibly related to participation in the research ("possibly related" means there is a reasonable possibility that the incident, experience, or outcome may have been caused by the procedures involved in the research); and
- Suggests that the research places participants or others at a greater risk of harm (including physical, psychological, economic, or social harm) than was previously known or recognized.

This study will use the OHRP definition of UP.

8.2 CLASSIFICATION OF AN ADVERSE EVENT

8.2.1 SEVERITY OF EVENT

All AEs will be assessed by the clinician using a protocol defined grading system. The protocol defined grading system to be used is:

- Mild Events require minimal or no treatment and do not interfere with the participant's daily activities.
- **Moderate** Events result in a low level of inconvenience or concern with the therapeutic measures. Moderate events may cause some interference with functioning.
- Severe Events interrupt a participant's usual daily activity and may require systemic drug therapy or other treatment. Severe events are usually potentially life-threatening or incapacitating.

8.2.2 RELATIONSHIP TO STUDY AGENT

All AEs will have their relationship to study agent or study participation assessed with a level of specificity appropriate to the study design. The clinician's assessment of an AE's relationship to study agent (drug) is part of the documentation process, but it is not a factor in determining what is or is not reported in the study. If there is any doubt as to whether a clinical observation is an AE, the event should be reported. All AEs must have their relationship to study agent assessed. In a clinical trial, the study product must always be suspect. To help assess, the following guidelines are used.

- **Related** The AE is known to occur with the study agent, there is a reasonable possibility that the study agent caused the AE, or there is a temporal relationship between the study agent and event. Reasonable possibility means that there is evidence to suggest a causal relationship between the study agent and the AE.
- Not Related There is not a reasonable possibility that the administration of the study agent caused the event, there is no temporal relationship between the study agent and event onset, or an alternate etiology has been established. OR For all collected AEs, the clinician who examines and evaluates the participant will determine the AE's causality based on temporal relationship and his/her clinical judgment. The degree of certainty about causality will be graded using the categories below.
 - 1. **Definitely Related** There is clear evidence to suggest a causal relationship, and other possible contributing factors can be ruled out. The clinical event, including an abnormal laboratory test result, occurs in a plausible time relationship to drug administration and cannot be explained by concurrent disease or other drugs or chemicals. The response to withdrawal of the drug (dechallenge) should be clinically plausible. The event must be pharmacologically or phenomenologically definitive, with use of a satisfactory rechallenge procedure if necessary.
 - 2. **Probably Related** There is evidence to suggest a causal relationship, and the influence of other factors is unlikely. The clinical event, including an abnormal laboratory test result, occurs within a reasonable time after administration of the drug, is unlikely to be attributed to concurrent, disease or other drugs or chemicals, and follows a clinically reasonable response on withdrawal (dechallenge). Rechallenge information is not required to fulfill this definition.
 - 3. **Possibly Related** There is some evidence to suggest a causal relationship (e.g., the event occurred within a reasonable time after administration of the trial medication). However, other factors may have contributed to the event (e.g., the participant's clinical condition, other concomitant events). Although an AE may rate only as "possibly related" soon after discovery, it can be flagged as requiring more information and later be upgraded to "probably related" or "definitely related," as appropriate.
 - 4. Unlikely to be related A clinical event, including an abnormal laboratory test result, whose temporal relationship to drug administration makes a causal relationship improbable (e.g., the event did not occur within a reasonable time after administration of the trial medication) and in which other drugs or chemicals or underlying disease provides plausible explanations (e.g., the participant's clinical condition, other concomitant treatments).

5. Not Related – The AE is completely independent of study drug administration, and/or evidence exists that the event is definitely related to another etiology. There must be an alternative, definitive etiology documented by the clinician

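### The three-event safety halt names only probably related events, and that category carries a dechallenge condition that does not fit the scheduled single injection (a small wording gap)

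*Combined protocol and SAP*

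**What the plan says.** **Causality (Section 8.2.2).** Five categories run from definitely related to not related. For *Probably Related* the conditions are joined by *and*; the last is that the event "follows a clinically reasonable response on withdrawal (dechallenge"). The entry closes with "Rechallenge information is not required to fulfill this definition". For *Definitely Related* the wording is softer: "The response to withdrawal of the drug (dechallenge) should be clinically plausible", with rechallenge where necessary. The section also frames how the categories are to be used: "In a clinical trial, the study product must always be suspect"; "To help assess, the following guidelines are used"; and causality is determined "based on temporal relationship and his/her clinical judgment".

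**Severity (Section 8.2.1).** The scale has three levels: Mild, Moderate and Severe. They carry no numbers.

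**Halting (Section 8.5).** Study agent is halted and enrolment stops after three grade 3 events determined to be probably related. The DSMB is told within 24 hours and meets ad hoc, and the FDA is informed of the temporary halt. A separate list of stopping criteria follows.

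**Dosing.** The Protocol Summary and Section 2.2 describe one injection. The schedule table in Section 7.3.2 marks administration at Visit 1 only.

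**The concern.** The three-event rule is the only safety trigger in the protocol with a fixed event count and a fixed sequence of actions. Whether it fires depends on a label, and the label has two weaknesses.

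First, only one causality category is named. Nothing says *or higher*, so on the literal text the events with the strongest evidence against the drug do not count.

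Second, that category includes a condition written for repeated dosing. After one injection there is no later dose to withhold. An assessor who considers the condition unmet may choose *Possibly Related*, which also does not count.

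Each participant is injected once, so a halt mainly protects people not yet enrolled. With a threshold of three, one severe drug-caused event labelled outside the counted category moves the trigger from the third such event to the fourth.

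**Working it through.** The plan states no operating characteristic for the halting rule, so there is no figure to reproduce. The check compares the text.

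**Step 1. Is dechallenge part of the definition?** In *Probably Related* it is joined by *and* to reasonable timing and to other causes being unlikely. Rechallenge is waived expressly and dechallenge is not, which invites the reading that dechallenge is needed.

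**Step 2. Can it be observed?** Administration is marked at 1 of 6 visits (Section 7.3.2). Under that schedule no dosing remains to stop. The condition can still be read as improvement once the drug has cleared, but Section 8.2.2 does not say so.

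**Step 3. Which categories count?** Two lie above *Possibly Related*: probably and definitely. Section 8.5 names 1 of the 2. Section 8.2.2 lets a possibly related event be upgraded later to either. On the literal text, an upgrade to probably adds the event to the count, while an upgrade to definitely does not.

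**Step 4. What else would catch a severe drug-caused event?**

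| Type of severe event | Other route | Depends on the probably related label? |
|---|---|---|
| Serious | One drug-related SAE is a stopping criterion (Protocol Summary, Section 8.5); Section 10.1.2 lists any SAE | No |
| Local intolerance or allergic reaction | Stopping criterion on first occurrence (Section 8.5) | No |
| Unexpected, at least possibly related, and pointing to greater risk | Unanticipated-problem reporting (Sections 8.1.3, 8.4.2) | No |
| Becoming more frequent, or reportable in the investigator's judgment | Prompt reporting within 7 or 14 days (Section 8.4.2) | No |
| Any | Suspension for unacceptable risk (Section 5.5); real-time monitoring and DSMB review (Section 8.6) | No |

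The first row covers many severe events. Section 8.2.1 says "Severe events are usually potentially life-threatening or incapacitating", and the SAE definition in Section 8.1.2 includes "a persistent or significant incapacity or substantial disruption of the ability to conduct normal life functions". What is left is mainly severe reactions that are non-serious, non-local and non-allergic. For these the three-event rule is the only fixed count; the other routes rely on judgment.

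**Step 5. Is single dosing certain?** Wording that implies a second injection, or patients returning for one, stands in at least six places:

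- Protocol Summary, stopping criteria
- Section 2.3.1, dose discussion (two injections)
- Section 6.1.4 (patients returning for injection)
- Section 7.3.1 (a first dose)
- Section 8.5, stopping criteria
- Section 10.1.2, stopping criteria

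If a second injection were intended, withholding it would give dechallenge a meaning after the first.

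**Step 6. Size.** The documents give no rate of severe reactions and no data on how assessors would grade them. Any probability of a missed halt would rest on assumed inputs, so none is given.

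**The case against.** The strongest reply is that no competent assessor would apply the text so literally. Section 8.2.2 opens by asking for a degree of detail that suits the study design, presents the categories as guidelines, and rests causality on timing and clinical judgment. Section 8.3 requires onset and resolution times, and Sections 2.1 and 2.3.2 note the drug's short half-life. Improvement after exposure ends can therefore be judged from data already collected. Because probably and definitely are successive upgrades, a rule that halts on three probable events but ignores three definite ones is an unlikely intention. This reply largely stands and keeps the point small. It does not remove it, because a halting rule should not need a charitable reading to work.

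Three stronger readings are tempting, and the documents do not support them:

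- *Probably Related can never be reached, so the halt is inoperative.* Nothing in Section 8.2.2 says the event must resolve or that a further dose must be withheld. The judgment wording allows the category to be used.
- *Severe drug reactions would go unnoticed.* The routes in Step 4 do not depend on that label, and Section 8.4.2 sends every SAE to the manufacturer whatever its cause. In fairness to the concern, some stopping criteria read like rules for one patient, but Section 5.5 makes them grounds for suspending the study.
- *Grade 3 is undefined.* Section 8.2.1 calls its scale a grading system, and the third of its three levels is Severe. The mapping is plain; naming the level is only tidier.

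**Conclusion.** The point holds as a minor correction to a safety rule. Read literally, Section 8.5 leaves out definitely related events, and the one category it counts contains a condition that does not suit the scheduled single injection. The exposure is confined mainly to severe reactions that are neither serious, local nor allergic, and even these remain open to investigator-judgment reporting and DSMB review. The size cannot be quantified from the documents.

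The conclusion about dechallenge assumes that the schedule table, the Protocol Summary's description of the agent and Section 2.2 are right about a single injection. The omission of definitely related events does not depend on that assumption.

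**What to change.** 1. **Section 8.5.** Count three severe adverse events judged probably or definitely related. Keep the threshold of three.
2. **Section 8.2.2.** State that dechallenge and rechallenge are not required for *Probably Related* or *Definitely Related* after a single injection. Causality is then judged on time of onset, clinical picture and alternative causes, including surgery. Resolution as the drug clears is supportive only.
3. **Secondary clean-up.** The sponsor confirms single dosing and then aligns the wording in the six places listed in Step 5. If two injections are in fact intended, the schedule needs correcting instead, and the new sentence in Section 8.2.2 should apply to events after the last injection.

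The cost is a few sentences, one phrase in the halting rule and a matching edit to the adverse event form. No patients, visits or procedures are added. The downside is that the halt may trigger slightly more readily. Because Section 8.5 does not restrict the count to the drug arm, that includes events in blinded placebo patients. The consequence is a temporary halt with DSMB review, not automatic termination.

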8.2.3 EXPECTEDNESS

Expected adverse reactions are AEs that are common and known to occur for the study agent being studied and should be collected in a standard, systematic format using a grading scale based on functional assessment or magnitude of reaction.

An AE or suspected adverse reaction is considered "unexpected" if it is not listed in the IB or is not listed at the specificity or severity that has been observed; or, if an IB is not required or available, is not consistent with the risk information described in the general investigational plan or elsewhere in the protocol or the USPI, as amended. For example, under this definition, hepatic necrosis would be unexpected (by virtue of greater severity) if the IB referred only to elevated hepatic enzymes or hepatitis. Similarly, cerebral thromboembolism and cerebral vasculitis would be unexpected (by virtue of greater specificity) if the IB listed only cerebral vascular accidents. "Unexpected," as used in this definition, also refers to AEs or suspected adverse reactions that are mentioned in the IB as occurring with a class of drugs or as anticipated from the pharmacological properties of the drug, but are not specifically mentioned as occurring with the particular drug under investigation.

The Principal Investigator will be responsible for determining whether an AE is expected or unexpected. An AE will be considered unexpected if the nature, severity, or frequency of the event is not consistent with the risk information previously described for the study agent.

8.3 TIME PERIOD AND FREQUENCY FOR EVENT ASSESSMENT AND FOLLOW-UP

The occurrence of an AE or SAE may come to the attention of study personnel during study visits and interviews of a study participant presenting for medical care, or upon review by a study monitor. All AEs including local and systemic reactions not meeting the criteria for SAEs will be captured on the appropriate CRF. Information to be collected includes event description, time of onset, clinician's assessment of severity, relationship to study product (assessed only by those with the training and authority to make a diagnosis), and time of resolution/stabilization as well as seriousness of the event. All AEs occurring while on study must be documented appropriately regardless of relationship. All AEs will be followed to adequate resolution.

Any medical condition that is present at the time that the participant is screened will be considered as baseline and not reported as an AE. However, if the study participant's condition deteriorates at any time during the study, it will be recorded as an AE. UPs will be recorded in the data collection system throughout the study.

Changes in the severity of an AE will be documented to allow an assessment of the duration of the event at each level of severity to be performed. AEs characterized as intermittent require documentation of onset and duration of each episode.

The PI will record all reportable events with start dates occurring any time after informed consent is obtained until 7 (for non-serious AEs) or 30 days (for SAEs) after the last day of study participation. At each study visit, the investigator will inquire about the occurrence of AE/SAEs since the last visit. Events will be followed for outcome information until resolution or stabilization.

8.4 **REPORTING PROCEDURES**

8.4.1 ADVERSE EVENT REPORTING

The Principal Investigator will assess the occurrence of AEs throughout the subjects' participation in the study. Subjects will be followed for toxicity for 30 days after treatment has been discontinued or until death, whichever occurs first. The clinical course of each event will be followed until resolution, stabilization, or until it has been determined that the study treatment or participation is not the cause.

The investigator is responsible for ensuring that all adverse events observed by the investigator or reported by the subject, which occur after the subject has signed the informed consent, are fully recorded in the subject's case report form, subject's medical records, and/or any other institutional requirement. Source documentation must be available to support all adverse events.

A laboratory test abnormality considered clinically relevant (e.g., causing the subject to withdraw from the study), requiring treatment or causing apparent clinical manifestations, or judged relevant by the investigator, should be reported as an adverse event.

The investigator will provide the following for all adverse events:

- Description of the event
- Date of onset and resolution
- seriousness of the event
- Attribution of relatedness to the investigational agent
- Action taken as a result of the event
- Outcome of event

The Principal Investigator will report adverse events to the IRB according to their policies and procedures in reporting adverse events.

8.4.2 SERIOUS ADVERSE EVENT REPORTING

Investigator Reporting to the FDA: Adverse reactions will be reported promptly to the Food and Drug Administration (FDA) via Medwatch by the Sponsor if the type of event is serious, unlisted/unexpected and possibly related to the study drug. A clear description of the suspected reaction will be provided along with an assessment as to whether the event is drug or disease related. The Sponsor will call the FDA as soon as he/she is aware (within ten (10) working days) that an adverse reaction has occurred. The phone number for the FDA is [contact].

The study sponsor will be responsible for notifying FDA of any unexpected fatal or lifethreatening suspected adverse reaction as soon as possible but in no case later than 7 calendar days after the sponsor's initial receipt of the information.

The Principal Investigator will complete an Internal Prompt Reporting Form within the following timelines:

EVENT	TIMELINE	
An Unanticipated problem involving risks to		
subjects or others	If the event is life-threatening, report within	
	7 calendar days of receipt of the information.	
1. Unexpected (in terms of nature, severity, or	Follow-up reports for these events should be	
frequency) given (a) the research procedures that	Submitted within 14 calendar days of receipt	
are described in the protocol-related documents,	of information.	
such as the IRB-approved research protocol and		
informed consent document; and	All other events/problems must be reported	
(b) the characteristics of the subject population	within 14 calendar days of the investigator's	
being studied;	receipt of the information	
2. Related or possibly related to participation in the		
research; and		
3. Suggests that the research places subjects or		
others at a greater risk of harm (including physical,		
psychological, economic, or social harm) than was		
previously known or recognized.		
All Research-Related Deaths	Immediately (i.e. within 48 hours) upon	
(anticipated/unanticipated)	receipt of information	
Other event that in the PI's judgment, warrants	If life-threatening, report within 7 calendar	
reporting or is in the best interest of the subject(s)	days of receipt of the information.	
(e.g., because it may affect the safety and/or welfare		
of subjects; it changes the risk level of the study; or	All other events/problems must be reported	
the frequency of the same event significantly	within 14 calendar days of the investigator's	
increases)	receipt of the information.	
Other unanticipated problems that impact the	If life-threatening, report within 7 calendar days of receipt of the information.	
conduct or integrity of the study (e.g. FDA Clinical		
hold or recall, published literature or data and safety	J	
monitoring board report impacting risk-benefit ratio,	All other events/problems must be reported	
FDA Form 483 or warning letter, investigator medical	within 14 calendar days of the investigator's	
license restriction or suspension, participant is	receipt of the information.	
incarcerated)	1	

All SAEs will be followed until satisfactory resolution or until the site investigator deems the event to be chronic or the adherence to be stable.

Sponsor Safety Reporting contact information:	
Name, degree, title:	[name], PhD
Institution Name:	University of Kentucky
Address:	[name]
[contact]
Email:	[contact]
[contact]

Name: [name] Address: [name] [contact] Email: [contact] [contact]

The reporting of serious adverse events to the study sponsor does not relieve the investigator from other regulatory reporting responsibilities.

Investigator reporting to SOBI: The Sponsor must inform Swedish Orphan Biovitrum (SOBI) in writing using a SOBI SAE or a MEDWATCH 3500A form of any SAE, independent of causality. The written report must be completed and supplied to SOBI by e-mail or facsimile within 24 hours/1 business day of first awareness. The initial report must be as complete as possible, including an assessment of the causal relationship between the event and the investigational product(s), if available. Information not available at the time of the initial report (e.g., an end date for the adverse event or laboratory values received after the report) must be documented on a follow-up report.

A final report to document resolution of the SAE is required. A copy of the email transmission of the SAE report to SOBI ([contact]) should be attached to the SAE and retained with the patient records.

SOBI Safety Reporting contact information:

Drug Safety Swedish Orphan Biovitrum [name] [contact] [contact] (switchboard) e-mail: [contact]

The reporting of serious adverse events to SOBi does not relieve the sponsor from other regulatory reporting responsibilities.

SOBi Safety Reporting contact information:

[contact]

e-mail: [contact]

